## 4.4.1 Key subgroup analysis

The key subgroup is the MCI subgroup, defined as 1.5 SD below the norm on the Baddeley reasoning test. Subgroup analysis will be performed by repeating the primary analysis and including a treatment by covariate interaction term for the MCI subgroup.

Further exploratory subgroups analyses are outlined in section 4.6.1.

Sensitivity analyses for the definition of cognitive impairment, for the multiple imputation and for the order of questions are outlined in section 4.6.2.

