## **Secondary Research Objectives:**

A key secondary research objective is to measure differences across trial arms in the change in the proportions of participants to a different category – either from no cognitive impairment to cognitive impairment (AACD or MCI), from AACD to MCI or severe cognitive impairment, or from MCI to severe cognitive impairment. The Baddeley verbal reasoning task will be used to indicate AACD (defined as scores more than 1 SD below the normative score\*),MCI (defined as scores more than 1.5 SD below the normative score\*) or severe cognitive impairment (defined as scores more than 2 SD below the normative score\*). These are study specific definitions rather than formal diagnostic criteria.

\*normative score determined by PROTECT database – large (n>15,000) cohort of older adults' data on battery of cognitive assessment tasks (https://www.protectstudy.org.uk/)

Additional secondary research objectives are to evaluate the effectiveness of the Active Brains digital intervention across a number of other key outcomes:

- 1. Instrumental Activities of Daily Living
- 2. Additional cognitive outcomes (including spatial working memory, attention, and verbal short-term memory)

\* Funding for five year follow-up is contingent on evidence of effectiveness in changing behaviour and improving cognition at 1 year.

- 3. Health-related quality of life
- 4. Patient enablement
- 5. Depression
- 6. Changes in the target behaviours (physical activity (including sedentary time), healthy eating, engagement with brain training games)
- 7. Mortality data

A complete list of measures is provided in table 2 at the end of the document.

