## **Eligibility Criteria**

When patients first register on the Active Brains study website they will answer a series of screening questions to make sure that they fit the study inclusion criteria below. Figure 1 outlines the participant identification and screening procedures.

To be eligible for inclusion, individuals with signs of cognitive decline will:

- Be aged between 60 and 85 years old inclusive
- Have cognitive impairment (AACD) defined as 1 SD below the norm on the Baddeley reasoning test [47]. A key subgroup is MCI, which will be defined simply as 1.5 SD below the norm on the Baddeley reasoning test. In statistical analysis we will also explore the impact in subgroups defined by alternative combinations of impairment in Baddeley reasoning, IADL and memory e.g. of MCI defined as 1.5SD below the norm in another non-memory cognitive domain plus memory impairment [5, 12, 13], and AACD defined as 1 SD below the norm for the Baddeley reasoning test [47] and IADL.
- Be willing and able to access the internet
- Not have an existing diagnosis of dementia at baseline
- Not report high levels of leisure time physical activity already (i.e. score 30 or more on the Godin Leisure Time Exercise Questionnaire (counting moderate or vigorous physical activity only)).
- Will not have a recorded diagnosis of long-COVID in their medical records at baseline

To be eligible for inclusion individuals without signs of cognitive decline will:

- Be aged between 60 and 85 years old inclusive
- Have normal cognitive function (i.e. do not meet criteria for cognitive impairment as defined above)
- Be willing and able to access the internet
- Not have an existing diagnosis of dementia at baseline

- Not report high levels of leisure time physical activity already (i.e. score 30 or more on the Godin Leisure Time Exercise Questionnaire (counting moderate or vigorous physical activity only)).
- Will not have a recorded diagnosis of long-COVID in their medical records at baseline

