#### 4.4 Primary endpoint

The Baddeley verbal reasoning score at 1 year will be analysed using linear regression, adjusting for baseline Baddeley verbal reasoning score and age, gender, IMD score, number of comorbidities and polypharmacy (yes/no). Adjustment for prognostic covariates, specified a priori, is now commonly recommended in the primary analysis of trial data and can potentially increase power [36, 37]. Assumptions for linear regression will be checked using QQ plots for normality and residual vs fitted value plots for linearity and homoscedasticity. If linear modelling assumptions are not met, the data will be transformed using, e.g., a Box Cox transformation and back transformed at values of interest.

The primary analysis will use multiple imputation with chained equations. The imputation model will include all variables in the analysis model and any baseline covariates predictive of

the Baddeley verbal reasoning score or its missingness. Predictors of missingness will be ascertained using Lasso regression [35]. Potential auxiliary variables will include all baseline variables. A model for outcome that includes randomised group, baseline outcome and all potential auxiliary variables will be fitted using the LASSO with 10-fold cross-validation [38]. The regularization penalty (denoted by  $\lambda$ ) will be chosen such that the cross-validation error was within one SE of the minimum [39]. The auxiliary variables that are included in the fitted model from the LASSO will be included in the imputation model for the outcome, i.e., the LASSO will used to select variables for the imputation model but not to estimate parameters of the imputation model. One hundred imputations will be performed and the imputed estimates will be combined using Rubin's rules. Imputation will be performed separately by randomised group and then combined [40].

All tests will be two-tailed with point estimates and 95% confidence intervals for the treatment effect presented. No formal adjustment for multiple significance testing will be applied. Analyses will be performed using Stata version 17 or above.

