## 4.6 Additional analyses

## 4.6.1 Subgroup analyses

For the primary outcome at 1 year, exploratory subgroup analyses will be performed by repeating the primary analysis and including a treatment by covariate interaction term for the following baseline subgroups:

Age: above/below 75 years

Gender: male/female

• Deprivation: IMD more deprived (deciles 1-5) vs less deprived (deciles 6-10)

Comorbidities: < 2 vs ≥ 2

Polypharmacy: number of medications ≥ 5 vs ≤ 4

Health diet: high/low prudent diet score (FFQ)

Physical activity: high/low IPAQ score

Depression: depression vs no depression, based on GDS at baseline

Retirement: retired/working

The same subgroups will be analysed in the same way using the primary outcome at 5 years.

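### Effect modification by baseline cognition is tested only through an MCI yes/no cut; adding a continuous baseline interaction beside it would give real power against a gradient

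*SAP*

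**What the plan says.** SAP 4.4.1 states: "The key subgroup is the MCI subgroup, defined as 1.5 SD below the norm on the Baddeley reasoning test". The test repeats the primary analysis, "including a treatment by covariate interaction term for the MCI subgroup". The cut acts inside a restricted range, because entry to the cognitive decline trial requires a low score already (Protocol, Eligibility Criteria: "Have cognitive impairment (AACD) defined as 1 SD below the norm on the Baddeley reasoning test"). The other trial contains no MCI participants, so the interaction can be estimated only in the cognitive decline trial or in a combined data set.

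SAP 4.6.1 adds nine subgroups for the primary outcome: "exploratory subgroup analyses will be performed by repeating the primary analysis and including a treatment by covariate interaction term". All nine have two levels. Seven divide a measured quantity: age ("Age: above/below 75 years"), IMD deciles, number of comorbidities, number of medications, prudent diet score, IPAQ ("Physical activity: high/low IPAQ score") and the GDS. No cut-point is given for diet or IPAQ. Gender and retirement are categorical by nature.

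The primary model in SAP 4.4 already contains the baseline Baddeley score, with no cut indicated. Neither document plans an interaction of treatment with a continuous covariate.

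**The concern.** Both background sections say that the value of the more intensive intervention may vary with the risk of dementia. That variation could well be gradual. A yes/no term treats a participant at -1.49 SD like one at -1.0 SD, and one at -1.51 SD like one at -3 SD. If benefit changes smoothly with baseline score, the cut discards part of the evidence, and a real gradient is more likely to be reported as no evidence of a subgroup difference. No diagnostic standard forces the cut: of the AACD, MCI and severe-impairment thresholds, the protocol says "These are study specific definitions rather than formal diagnostic criteria". The uncut score is already collected and already in the model, so the lost information could be recovered without new data.

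**Working it through.** **Inputs from the documents.** Entry at 1 SD and MCI at 1.5 SD below the norm; two-sided alpha 0.05; standardised effect 0.15; 698 MCI and 698 AACD per arm, so 1396 (SAP 2.2); recruitment of 3647 per arm (SAP 2.2); 70% follow-up at 1 year (Protocol, sample size), so 3647 × 0.70 = 2553 per arm.

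**The plan's own figure.** 2 × (1.960 + 0.842)² / 0.15² = 697.7, rounded up to 698 per group. This agrees. The documents give no power figure for any interaction test, so there is none to reproduce.

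**Assumptions.** Baseline score is standard normal in the norm population and truncated at -1 SD in the trial; residual SD of the outcome is 1; two arms are compared; the effect is linear in baseline score, with a slope that makes the average MCI and AACD effects differ by 0.15 SD. None of these comes from the documents. The 0.15 gap is borrowed from the plan's target main effect.

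**Information kept by the cut.** Relative to a linear interaction this is r², the squared correlation between the score and its MCI indicator.
- Proportion MCI: p = Φ(-1.5)/Φ(-1) = 0.421, so p(1-p) = 0.2438.
- Mean score: -1.939 in MCI and -1.224 in AACD, a difference of 0.714. SD of the truncated score: 0.446.
- r = 0.714 × √0.2438 / 0.446 = 0.790, so r² = 0.625. The loss is 37.5%, and 1/0.625 = 1.60 times the sample would be needed.

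**Power if the trend is linear.** The slope per within-trial SD is (0.15/0.714) × 0.446 = 0.0937. The standard error is √(2/n) for the continuous term and √(2/(n × 0.2438)) for the cut. Power is Φ(z - 1.96).

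| Analysed per arm | Cut: SE, z, power | Continuous: SE, z, power |
|---|---|---|
| 1396 | 0.0767, 1.96, 50% | 0.0379, 2.48, 70% |
| 2553 | 0.0567, 2.65, 75% | 0.0280, 3.35, 92% |

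Simulation with 1500 runs gave 49.3% against 69.5%, and 75.5% against 90.8%.

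**Power if the truth is a step of 0.15 SD at -1.5 SD.** The cut is now the correct model and the continuous term's z is r times as large. At 2553 this gives 2.65 against 2.09, or 75% against 55% (simulated 77% against 56%). At 1396 it gives 1.96 against 1.55, or 50% against 34%.

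**Sensitivity of the MCI loss to the assumed shape.** Score floors between -2 and -4 SD give 28-37%. Shifting the population mean between -1 and +0.5 SD gives 35-48%. Uniform scores give 25-44%. An even MCI/AACD mix gives 40%. If the two trials are pooled at about the planned sizes, an MCI term groups AACD with the unimpaired and the loss is about 62-63%.

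**Loss for the exploratory cuts, if linear.**

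| Modifier | Assumed shape | Loss |
|---|---|---|
| Any normal measure | split 50:50 to 20:80 | 36-51% |
| Age at 75 | uniform; other shapes | 28%; 38-60% |
| IMD halves | even; skewed to less deprived | 24%; 31% |
| Comorbidities at 2 | Poisson mean 1-3 | 30-58% |
| Medications at 5 | most cases; few taking 5 or more | 35-44%; up to 67% |
| IPAQ at median | exponential; lognormal | 52%; 73% |
| GDS | illustrative score distributions | 20-22% |
| Gender, retirement | categorical | none |

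**The case against.** The strongest reply is that MCI against AACD is a design stratum. SAP 2.2 sizes the cognitive decline trial separately for the two groups, the eligibility criteria name MCI as a key subgroup, and the key secondary endpoint uses the same thresholds. Treatment by MCI answers the prespecified question of whether the effect differs between those strata. This stands, and it is why the contrast should not be replaced.

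Second, the documents do not establish a gradient. The protocol background reports conversion to dementia from AACD at rates close to those from MCI, and similar training effects among people with AACD. A linear term can also lose as much power as it gains, as the step calculation shows. This stands too: neither test is best in every case.

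Third, the exploratory tests are labelled as such, and the alternative MCI and AACD definitions in SAP 4.6.2 widen the look at baseline cognition. That limits the consequences, but those definitions are still categorical and do not test a gradient.

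Three stronger readings are tempting and not supported. A reader might infer that every subgroup test loses some fixed share, such as 35-50%; the losses run from none to about 70%, and all rest on assumed shapes. A reader might infer that the planned test would probably miss a gradient; at planned recruitment it has about 75% power for the one assumed here, and the 50% figure applies only at the bare Baddeley requirement of 1396. A reader might also infer that the study-specific thresholds make the cut improper; they are prespecified and tied to the sample size.

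**Conclusion.** The point holds as a cheap improvement, not as an error. Dependence of benefit on baseline cognition is tested only through categories, and a gradual trend would be tested with roughly 37% less information than the collected data allow (25-48% over the shapes assumed within the cognitive decline trial). The corresponding power difference is 75% against 92% at 2553 per arm. These figures require linear effect modification, a truncated normal score and a residual SD of 1; under a step at the MCI threshold the advantage passes to the planned test. For the seven exploratory cuts the loss is roughly 20-70% depending on shape. The baseline score remains an uncut covariate in the main model, so the primary treatment comparisons and the stated sample sizes are untouched.

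**What to change.** In SAP 4.4.1, keep the prespecified treatment by MCI contrast. Add beside it a treatment by continuous baseline Baddeley interaction, with a non-linear term as a check, and report model-based effects with confidence intervals at representative AACD and MCI scores. In SAP 4.6.1, test age, IMD, comorbidity count, medication count, diet score, IPAQ (logged or ranked) and GDS on their measured scales, and keep the listed cuts for the subgroup display.

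The cost is SAP wording and a few model terms, with no new data. Imputation is already planned separately by arm and includes the analysis-model variables, so it accommodates a linear treatment by baseline interaction; any curve terms should be included as well. The downsides are one more key interaction test to interpret and an assumed linear trend unless a curve is fitted. The SAP should say in advance how the two key interaction results will be read if they differ.

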#### 4.4.2 Adherence to intervention

To explore the effect of adherence to the randomised intervention, we will estimate the treatment effect among the subpopulation of participants would adhere with the intervention under either treatment assignment. The estimand is defined in Table 2, and adherence with the intervention is defined as:

1) Completing the first session of Active Brains as far as the pages that advise on what to do (Active Lives homepage)

AND

2) Adhering to at least some of the recommended behaviours, defined as answering 'less than a month' or more of at least one of the Getting Active/Strength and Balance/Breaks from Sitting/Eat for Health recommendations.

OR

3) Accessed Brain Training more than once

Table 2. Intercurrent events and estimands

Population	All trial participants eligible at baseline
Treatment	Active Brains + Support vs Active Brains vs usual care
Endpoint	Baddeley verbal reasoning score at 1 year
Summary measure	Mean difference for intervention vs usual care
Intercurrent event	Strategy for handling intercurrent event
Did not complete core	Principal stratum
sections of Active Brains	- subpopulation of patients who would complete core
intervention	sections of the intervention under either treatment
	assignment

This will be estimated using a Complier Average Causal Effect (CACE) analysis. The CACE analysis will be carried out using instrumental variables regression, with randomised group as the instrumental variable, and adherence defined above as the endogenous variable.

#### 4.5 Secondary endpoints

The following secondary outcomes will be analysed at 1 and 5 years:

#### 4.5.1 Key secondary endpoint

Change in the proportions of participants to a different category:

- from no cognitive impairment to cognitive impairment (AACD or MCI),
- from AACD to MCI or severe cognitive impairment,
- from MCI to severe cognitive impairment.

The Baddeley verbal reasoning task will be used to indicate AACD (defined as scores more than 1 SD below the normative score), MCI (defined as scores more than 1.5 SD below the normative score), and severe cognitive impairment (defined as scores more than 2 SD below the normative score). The normative score is determined by PROTECT database, a large (n>15,000) cohort of older adults' data on battery of cognitive assessment tasks (https://www.protectstudy.org.uk/)

### 4.5.2 Cognitive performance tests

Cognitive performance tests include:

- Spatial Working Memory (measured using Self ordered search test)
- Digital Vigilance (attention measured using the 'digit' span task)
- Verbal Short-term memory (measured using the paired associates learning)

These are continuous scores and will be analysed in the same way as the primary outcome, adjusting for the baseline test score and the same covariates as in the primary analysis.

## 4.5.3 Informant Questionnaire on Cognitive Decline in the Elderly

Modified version of Informant Questionnaire on Cognitive Decline in the Elderly (IQCODE SF) consists of 16 questions with a Likert response ranging from 1=much improved to 5=much worse. An overall change score is calculated by averaging the scores on each item. This score will be analysed using linear regression adjusting for baseline IQCODE score and the same covariates as in the primary analysis.

#### 4.5.4 Patient Enablement Index (PEI)

Patient Enablement Index (PEI) consists of six questions and produces a mean score ranging from 1 to 7 with lower scores indicating higher enablement. The PEI score will be analysed using linear regression adjusting for the same covariates as in the primary analysis.

## 4.5.5 Instrumental Activities of Daily Living (IADL)

Instrumental Activities of Daily Living (IADL) consists of 7 questions, each with two parts, about managing day to day activities. The first part of each question rates how well these activities can be managed 0=On my own; 1=With some help; 2=With full help; 3 = Could not do it (so it wasn't done at all or someone did it for me); 8=Not relevant to me (always done by someone else or not needed). The second part of each question rates how difficult it is (or would be) to do the activity with 0=No difficulty; 1=Some difficulty; 2=Great difficulty. The total score is the sum of all the subscales, creating a score from 0 to 35. The total IADL score will be analysed using linear regression, adjusting for the same covariates as in the primary analysis.

## 4.5.6 International Physical Activity Questionnaire (IPAQ)

International Physical Activity Questionnaire (IPAQ) plus strength and balance items

MET minutes achieved in each category (walking, moderate activity and vigorous activity) and total MET minutes of physical activity a week are calculated as follows:

- Walking MET-minutes/week = 3.3 \* walking minutes \* walking days
- Moderate MET-minutes/week = 4.0 \* moderate-intensity activity minutes \* moderate days
- Vigorous MET-minutes/week = 8.0 \* vigorous-intensity activity minutes \* vigorousintensity days
- Total physical activity MET-minutes/week = sum of Walking + Moderate + Vigorous MET-minutes/week scores.

Note: Bouts of activity lasting less than 10 minutes duration are not counted. It is also recommended that activity bouts of greater than 3 hours are truncated, i.e., in each category a maximum of 21 hours of activity are permitted a week (3 hours X 7 days).

Total MET minutes will be analysed using linear regression adjusting for baseline MET minutes and the same covariates as in the primary analysis.

## 4.5.7 Quality of Life (EQ5D)

Quality of Life (EQ5D) EQ-5D-5L index values will be derived using the appropriate value set. These utility scores will be analysed using linear regression adjusting for baseline EQ5D score and the same covariates as in the primary analysis.

## 4.5.8 Short Warwick Edinburgh Mental Well-Being Scale (SWEMWBS)

Short Warwick Edinburgh Mental Well-Being Scale (SWEMWBS) is a 7-item scale on a Likert scale 1=none of the time to 5=all of the time. It is scored by first summing the scores for each of the seven items. The total raw scores are then transformed into metric scores using the SWEMWBS conversion table which can be found here:

https://warwick.ac.uk/fac/sci/med/research/platform/wemwbs/using/howto/swemwbs r aw score to metric score conversion table.pdf

Interpretation: Scores range from 7 to 35 and higher scores indicate higher positive mental wellbeing. To see how individual's scores compare with national survey data (from adults) which can be found here:

https://warwick.ac.uk/fac/sci/med/research/platform/wemwbs/using/howto/wemwbs population norms in health survey for england data 2011.pdf

The metric scores will be analysed using linear regression adjusting for baseline SWEMWBS score and the same covariates as in the primary analysis.

## 4.5.9 12-Item Short Form Health Survey (SF12)

The 12-Item Short Form Health Survey (SF12) is a self-reported quality of life measure assessing the impact of health on an individual's everyday life. Two summary scores are reported from the SF-12 – a mental component score (MCS-12) and a physical component score (PCS-12). The scores may be reported as Z-scores (difference compared to the population average, measured in standard deviations). The population average PCS-12 and MCS-12 are both 50 points. The population standard deviation is 10 points, so each 10 increment of 10 points above or below 50, corresponds to one standard deviation away from the average. The MCS-12 and PCS-12 scores will be analysed using linear regression, adjusting for the baseline scores and the same covariates as in the primary analysis.

## 4.5.10 Diagnosis of dementia

Diagnosis of dementia will be obtained from notes review. This will be analysed using logistic regression, adjusting for the same covariates as in the primary analysis.

The primary definition of dementia will be based on:

1. If there is a notes diagnosis of dementia participants will be classed as having dementia.

As sensitivity analyses, we will use the following methods to ascertain the dementia outcome:

- 2. As recording in notes is suboptimal, consider self-report item "Has a doctor or other medical worker ever said that you have dementia?" (Y/N) this data currently collected in baseline and year 1 and year 5 follow-up online/paper measures.
- 3. Evidence of significant decline in Baddeley (baseline to follow-up) **AND** evidence of functional deterioration (**EITHER**: a) significant change in self-report IQCODE (baseline to follow-up) **OR** b) two self-report questions on difficulty in finance and planning\* (NB the Caerphilly study was based on informant not self-report). Difficulty in finance and planning items collected in year 5 online/paper measures.

